#### 9.8.2 CM classification

Rules presented in Table 2 will be used for the classification of medications and other procedures as concomitant or previous. A medication can simultaneously be concomitant and previous in cases where medication started prior to treatment but it is ongoing at baseline.

Table 2 CM Classification rules

	Start date of CM		Concomitant classification	Previous classification
Day	Month	Year		
UNK	UNK	UNK	Concomitant if Ongoing Not concomitant if not Ongoing	Previous
UNK	UNK	< Treatment start (year)	Concomitant if Ongoing Not concomitant if not Ongoing	Previous
UNK	UNK	≥ Treatment start (year)	Concomitant	Not previous
UNK < Treatment start (month and year)		ent start (month and year)	Concomitant if Ongoing Not concomitant if not Ongoing	Previous
UNK	UNK ≥ Treatment start (month and year)		Concomitant	Not previous
< Treat	< Treatment start (complete date)		Concomitant if Ongoing	Previous

Start date of CM		Start date of CM	Concomitant classification	Previous classification
Day	Month	Year		
			Not concomitant if not Ongoing	
≥ Treatment start (complete date)		(complete date)	Concomitant	Not previous

CM = Concomitant medications; UNK = Unknown

### 9.9 Scoring of HRQoL Data

Unless otherwise specified, Health-Related Quality of Life (HRQoL) questionnaires will be scored using their published administration and scoring manual. For items with missing responses, the response will be managed as per the scoring manual.

#### 9.9.1 MSIS-29

The Multiple Sclerosis Impact Scale (MSIS-29) is a 29-item self-report measure with 20 items associated with a physical scale and 9 items with a psychological scale. Items ask about the impact of multiple sclerosis (MS) on day-to-day life in the past two weeks. All items have 5 response options: 1 "not at all" to 5 "extremely". Each of the two scales are scored by summing the responses across items, then converting to a 0-100 scale where 100 indicates greater impact of disease on daily function (worse health) (RIMS - Rehabilitation in Multiple Sclerosis, s.d.).

The physical impact score is computed by summing items number 1-20 inclusive (observed score). This score can then be transformed to a score on a scale of 0-100 using the formula below:

$$\frac{[100 \times (observed\ score - 20)]}{(100 - 20)}$$

The psychological impact score is computed by summing items number 21-29 inclusive (observed score). This score can then be transformed to a score on a scale of 0-100 using the formula below:

$$\frac{[100 \times (observed\ score - 9)]}{(45 - 9)}$$

For respondents with missing data, but where at least 50% of the items in a scale have been completed, a respondent–specific mean score computed from the completed items can be computed. This is achieved by calculating an average score from the available items and assign this average score to the missing items. Then, the normal score as per the formulas above can be calculated (RIMS - Rehabilitation in Multiple Sclerosis, s.d.).

## 9.9.2 TSQM v1.4

Version 1.4 of the TSQM consists of 14 items that results in four specific domains: Effectiveness, Side Effects, Convenience, and one global scale item, Global Satisfaction. Scores for each domain are computed by adding the TSQM items in each domain and then transforming the composite score into a value ranging from 0 to 100. Of note, a score can be computed for a domain only if no

2.0

more than one item is missing from that domain. The calculations specific to each domain are presented in detail below (IQVIA, 2019).

#### **Global Satisfaction**

•  $([(Sum (Item 12 to Item 14)) - 3] divided by 14) \times 100$ 

If Item 12 or 13 is missing

• ([(Sum (the two completed items)) – 2] divided by 10)  $\times$ 100

If Item 14 is missing

• ([(Sum (Item 12 and Item 13)) -2] divided by 8)  $\times$  100

#### **Effectiveness**

• ([(Item 1 + Item 2 + Item 3) – 3] divided by 18)  $\times$  100

If one item is missing

• ([Sum (the two completed items)) -2] divided by 12)  $\times$  100

#### **Side Effects**

If Question 4 is answered 'No'

• Score = 100

If Question 4 is not answered 'No'

• ([Sum (Item 5 to Item 8) -4] divided by 16)  $\times$  100

If one item is missing

• ([(Sum (the three completed items)) - 3] divided by 12)  $\times$  100

#### Convenience

• ([Sum (Item 9 to Item 11) - 3] divided by 18)  $\times$  100

If one item is missing

• ([(Sum (the two completed items) -2] divided by 12)  $\times 100$ 

## 10 Study Patients

The subsections in this section include specifications for reporting participant disposition and study treatment/study discontinuations. Additionally, procedures for reporting protocol deviations are provided.

## 10.1 Disposition of Patients and Discontinuations

The number and percentage of patients in each of the below disposition categories will be presented. Percentages will be presented with respect to the number of treated patients.

- Total number of patient entered, based on completion of "Study Entry" eCRF form and reason for screen failure
- Number and percentage of enrolled patients
- Number and percentage of non-treated
- Number and percentage of treated patients (i.e. patients who gave informed consent and received at least one dose of cladribine). This is the same group of patients as FAS

The end of study status will be summarized for FAS by:

- Number and percentage of patients who completed the 24-Months follow-up period
- Number and percentage of patients who early discontinued the study (overall and by primary reason)

The end of treatment status will be summarized for FAS overall and independently for each of the end of study status groups by:

- Number and percentage of treated patients who completed study treatment (overall and by reason)
- Number and percentage of treated patients who permanently discontinued the study treatment (overall and by primary reason)

Length of follow-up, defined as date of last contact – study treatment start date + 1 will be reported for FAS overall and by end of study status.

Disposition of patients by expected follow-up visit attendance will also be presented for each of the expected visit schedule as defined in IAP Section 9.5.

Disposition of patients will be presented overall and by Country and Site level.

All disposition information described above will be listed, including relevant disposition dates (informed consent date, follow-up visit dates, date of last contact). A separate listing with death details will also be presented (date of death, primary reason for dead and autopsy details if available).

### 10.2 Protocol Deviations/Exclusion from Analysis Populations

## **10.2.1 Important Protocol Deviations**

Important protocol deviations (IPDs) are protocol deviations that might significantly affect the completeness, accuracy, and/or reliability of the study data or that might significantly affect a participant's rights, safety, or well-being. Since this is a non-interventional study and all procedures will be performed as per clinical practice, deviation from the expected schedule of assessments as presented in the Protocol Section 9.2.4 are not considered IPDs.

The list of potential protocol deviations is available at Appendix 18.1 according to the study Protocol Deviation Plan version 1.0 from 21 November 2019.

A frequency table with all IPDs based on FAS will be presented.

## 10.2.2 Reasons Leading to the Exclusion from an Analysis Population

This study only considers one analysis population (FAS). The only reason for not being included in FAS is by not receiving a cladribine dose although there is a prescription for it as per the study inclusion criterion 4 as defined in Protocol Section 9.2.1. This will be summarized in the disposition table as defined in IAP Section 10.1.

### 11 Demographics and Other Baseline Characteristics

If not stated otherwise, the following analyses will be performed based on the FAS.

## 11.1 Demographics

Demographic characteristics and physical measurements will be summarized descriptively using the following information from the baseline visit eCRF pages.

The following demographic characteristics will be included:

- Sex: Male, Female
- Race: Caucasian, Black or African American, Asian, American Indian or Alaska Native, Native Hawaiian or Pacific Islander, Other, not collected due to local regulations
- Age (years) at informed consent
- Age categories:
  - o <65 years
  - $\circ$   $\geq$ 65 years
    - **65-74**
    - **5** 75-84
    - ≥85 years
- Country

## 11.2 Medical History

The medical history will be summarized from the "Medical History" eCRF page, using the most recent Medical Dictionary for Regulatory Activities (MedDRA) version at the time of database lock, preferred term as event category and system organ class (SOC) body term as body system category. Each participant will be counted only once within each preferred term (PT) or SOC.

Medical history will be displayed in terms of frequency tables by six main categories as collected in the eCRF: any medical history, Relapsing-Remitting Multiple Sclerosis (RRMS) related medical history, ongoing medical history (severe/moderate/mild). Under each category, frequencies will be displayed by condition type (Malignancy, Severe Opportunistic Infection and Other relevant conditions) and under each condition type by primary SOC and PT in alphabetical order.

A listing will also be presented with all conditions reported.

#### **Other Baseline Characteristics** 11.3

#### 11.3.1 **Disease Characteristics**

Information on disease characteristics collected at baseline will be summarized. Summary statistics will be presented for:

- Disease duration (Months) = (ICF date Initial MS diagnosis date +1)
- Reason for switching to Cladribine treatment
- Baseline Magnetic Resonance Imaging (MRI) results:
  - Time since last MRI defined as ICF date Date of last MRI scan + 1
  - Total number of T1 Gd+ lesions
  - Total number of T2 lesions
  - Total Number of CUA Lesions

A Listing will be presented with all disease characteristics.

#### 11.3.2 **Previous MS medication history**

#### 11.3.2.1 **Previous DMD history**

Information on the most recent previous DMD medication will be summarized as number and percentage of patients under each specific DMD as collected in eCRF MS Medication History and grouped as described in IAP Section 8.2. For each DMD, treatment duration and reason for switching to Cladribine treatment will be described.

A listing will be created with most recent previous DMD medication, including the DMD name, start date, stop date and reason for switching to Cladribine treatment.

#### 11.3.2.2 Immunosuppressive/immunomodulatory agents history

percentage of patients who have ever been treated immunosuppressive/immunomodulatory agents will be described, overall and by treatment status at baseline (ongoing and previous immunosuppressive/immunomodulatory). For those who have a history of previous immunosuppressive/immunomodulatory agents, the number and percentage of patients under each preferred name of the specific reported agent(s) coded using the most recent World Health Organization Drug Dictionary (WHO-DD) and the treatment duration will be reported. Treatment duration (Months) will be calculated as treatment stop date – treatment start date +1 for previous medications and ICF date – treatment start date +1 for ongoing medications.

All reported previous immunosuppressive/immunomodulatory agents will be listed.

### 12 CMs/Procedures

The following analyses will be performed based on the FAS.

**CMs** are medications, other than study treatment, which are taken by patients any time during the on-treatment period.

**Previous medications** are medications, other than study treatment and pre-medications for study treatments, which started before the first administration of study treatments.

A medication may be classified as both concomitant and previous. The respective flags will be derived based on the start date as per the rules specified in IAP Section 9.8.2.

Concomitant and previous treatment each will be summarized by number and percentage of patients from the "CMs Details" CRF. Anatomical Therapeutic Chemical classification (ATC)-2nd level and preferred term will be tabulated as given from the WHO-DD most current version. If any previous or concomitant medication is classified into multiple ATC classes, the medication will be summarized separately under each of these ATC classes. The summary tables will be sorted by decreasing frequency of drug class and decreasing frequency of drug name in a given drug class. In case of equal frequency regarding drug class (respectively drug name), alphabetical order will be used. In case any specific medication does not have an ATC classification level 2 coded term, it will be summarized under "Unavailable ATC classification" category. Each participant will only be counted once, even if he/she received the same medication at different times.

All **concurrent procedures**, which were undertaken during the on-treatment period will be summarized according to the CRF page "Concomitant Procedures". Concurrent procedures will be MedDRA coded. Number and percentage of patients with concurrent procedures (Prior, on or after the first day of study treatment) overall and by type of procedure (as classified by medical review) will be presented.

Two separate listings will be created, one including all medications reported and other for all procedures reported.

## 13 Study Treatment: Adherence and Exposure

The following analyses will be performed based on the FAS. All dosing calculations and summaries will be based on "Cladribine Administration" CRFs pages.

Cladribine is administered in the first 2 weeks of each the 2 years of treatment planned. Therefore, it is not accurate to report treatment duration based on the date of last cladribine administration. Cladribine treatment exposure will then be summarized as number and percentage of patients who completed the treatment overall and for each of the 4 treatment courses (Year 1: Week 1, Year 1: Week 2, Year 2: Week 1 and Year 2: Week 2). Overall and for each treatment course, the number and percentage of patients with dose delays or dose changes will be reported, including the associated reasons. Number and percentage of patients who permanently discontinued the treatment and associated reasons for discontinuation will also be reported.

Cladribine utilization and adherence will be summarized for each treatment course (Year 1: Week 1, Year 1: Week 2, Year 2: Week 1 and Year 2: Week 2) and overall. For each treatment course, the following information will be presented:

- Dose, calculated as Number of tablets taken × 10/Weight (kg) at time of prescription
- Number of tablets prescribed
- Number of tablets taken
- Adherence to treatment, calculated as 100 × Taken tablets/Prescribed tablets. Adherence will also be presented under the following categories
  - <60%
  - 0 [60%-80%]
  - 0 [80%-90%]
  - o [90%-100%]

For the overall summary, the cumulative dose will be presented instead of dose. The cumulative dose will be calculated as the sum of all doses from all available treatment courses prior to treatment discontinuation or end of the 2 years treatment period.

## 14 Effectiveness Analyses

The following analyses will be performed based on the FAS except when otherwise stated.

## 14.1 Primary Outcome ARR

The primary outcome for this study is the difference in ARR between the pre-baseline 12-month period and over the 12 months period before the End of Study follow-up (2 years).

Relapses will be diagnosed by the treating physicians, as per routine clinical practice; a typical definition within this context is the appearance of new symptoms or the exacerbation of pre-existing symptoms that are attributed to MS and occur over a minimum of 24 hours and separated from a previous attack by at least 30 days, in the absence of fever or infection.

# 14.1.1 Primary Objective: Derivation and analysis of the Primary Outcome ARR

#### **Derivations**

Pre-baseline ARR will be defined as a total number of relapses reported in the last 12 months prior to Cladribine treatment as collected in the "12 Month Historical MS Data".

Twelve month period before the End of Study follow-up (2 years) ARR will be calculated as the sum of the number of MS relapses reported at Visit 3 and Visit 4 divided by the number of days between Visit 4 date and Visit 2 date and multiplied by 365.25. If a patient discontinues the study prior to Visit 4, it will be set to missing and excluded from the primary analysis.

For other study visits, ARR will be calculated similarly including data from the last 2 visits, except for ARR at Visit 1 for which only the last 6-month data will be included, and the annualized rate will be adjusted as per the formula described above. For ARR at Visit 1 and Visit 2, Cladribine start date will be used as the date to calculate the number of days elapsed.

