- EDSS, T25FW, 9-HPT, T25FW and 9HPT are optional and will be performed if done as per routine practice.
- Safety recording and reporting
- Upon availability: and MRI (total number of T1 Gd+, T2 and CUA lesions). These
 assessments are not mandatory parts of this study however we kindly ask for providing the
 scores in case the tests were carried out due to medical reasons or as part of the clinical
 routine.

Visit 3 assessments (V3, indicative Month 18)

- · Total number of relapses while in study, up until this visit
- Date of administration of therapy with Cladribine tablets and number of tablets taken versus prescribed dose
- Concomitant treatments
- TSQM-v1.4 Questionnaire: to be answered by the subject

- EDSS, T25FW, 9-HPT, T25FW and 9HPT are optional and will be performed if done as per routine practice
- · Safety recording and reporting
- CC

Visit 4 assessments (V4, indicative Month 24)

- · Total number of relapses while in study, up until this visit
- Concomitant treatments
- . TSOM-v1.4 Questionnaire: to be answered by the subject
- · MSIS-29 Questionnaire: to be answered by the subject
- · EQ-5D-3L Questionnaire: to be answered by the subject
- EDSS, T25FW, 9-HPT, T25FW and 9HPT are optional and will be performed if done as per routine practice.
- · Safety recording and reporting
- CC

A patient is considered to have completed the study after they have had a follow-up visit at the end of the observation period of 24 months. Study termination earlier than month 24 may occur due to lost to follow up, informed consent withdrawal or any other reasons as recorded. Following assessments will be performed at study termination, if this information is available:

- Weight
- Total number of relapses while in study
- TSQM-v1.4 Questionnaire: to be answered by the subject
- MSIS-29 Questionnaire: to be answered by the subject
- CCI
- EDSS, T25FW, 9-HPT, T25FW and 9HPT are optional and will be performed if done as per routine practice.
- Safety recording and reporting
- Upon availability: MRI (total number of T1 Gd+, T2 and CUA lesions). These assessments
 are not mandatory parts of this study however we kindly ask for providing the scores in case
 the tests were carried out due to medical reasons or as part of the clinical routine.

For patients lost to follow up observations will be censored and will be handled as defined in the SAP. Lost-to follow-up is confirmed when at least 3 documented attempts to reach out the

Cladribine

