## 7 Changes to the Planned Analyses in the Clinical Study Protocol

There are no changes to the analyses planned per protocol.

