## 14.1.2 Sensitivity Analyses of the Primary Outcome ARR

A sensitivity analysis will be conducted using two different methods for missing data imputation, to assess the robustness of the primary analysis described above.

The first method will include a Last Observation Carried Forward (LOCF) approach, for which the last available ARR from previous visits will be used for the analysis.

The second method will include a Baseline Observation Carried Forward (BOCF) for which missing data for post-baseline ARR will be imputed as the pre-baseline ARR.

Both summary statistics and statistical results will be presented in the same table as the primary analysis. These sensitivity analyses are considered as supportive of the primary analysis.

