## 14.2.1 Secondary Objective: Derivation and analysis of the Secondary Outcome ARR

#### **Derivations**

Pre-baseline ARR will be defined as the total number of relapses reported in the last 12 months prior to Cladribine treatment as collected in the "12 Month Historical MS Data".

Twelve month period after the start of Cladribine treatment ARR will be calculated as the sum of the number of MS relapses from Visit 1 and Visit 2 divided by the number of days between Visit 2 data and start date of Cladribine and multiplied by 365.25. If a patient discontinues the study prior to Visit 2, it will be set to missing and excluded from the primary analysis.

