#### 16.4 Other Outcome MRI Lesions

# 16.4.1 Other Outcome MRI Lesions: Derivation and analysis of the Other Outcome MRI Lesions

#### **Derivations**

No derivations will be performed on this outcome. Data reported on "MRI and Relapse Count" and "12 Month Historical MS Data" CRF pages will be reported as collected.

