## 18.2 List of Interim Analysis Outputs

18.2	List of Interim Analysis Outputs
Output Number	Output Title
Table 15.1.1.1	Subject Disposition Status
Table 15.1.4.1	Demographic Characteristics – FAS Analysis Set
Table 15.1.6.1	Disease History – FAS Analysis Set
Table 15.1.6.3	Immunosuppressive/immunomodulatory history
Table 15.2.2.1.1	ARR comparison between Baseline and 12-Months after start Cladribine
	treatment – FAS Analysis Set
Table 15.2.2.2	ARR comparison between Baseline and 12-Months after start Cladribine
	treatment by Baseline DMD treatment – FAS Analysis Set
Figure 15.2.2.1	Forest Plot of ARR comparison between Baseline and 12-Months after
	start Cladribine treatment by Baseline DMD – FAS Analysis Set
Table 15.2.3.2	6-Month Disability Progression at Visit 1 (6-Months Follow-up), Visit 2
	(12-Months Follow-up) and Visit 3 (18-Months Follow-up) – FAS
	Analysis Set (Limited to Visit 2)
Table 15.2.3.5	6-Month Disability Progression at Visit 1 (6-Months Follow-up), Visit 2
	(12-Months Follow-up) and Visit 3 (18-Months Follow-up) by Baseline
	DMD treatment – FAS Analysis Set (Limited to Visit 2)
Figure 15.2.3.1	Bar Plot of 6-Month Disability Progression by Visit (Overall and by
	Baseline DMD) – FAS Analysis Set (Limited to Visit 2)
Table 15.2.4.2	6-Month Disability Improvement at Visit 1 (6-Months Follow-up), Visit
	2 (12-Months Follow-up) and Visit 3 (18-Months Follow-up) – FAS
	Analysis Set (Limited to Visit 2)
Table 15.2.4.4	6-Month Disability Improvement at Visit 1 (6-Months Follow-up), Visit
	2 (12-Months Follow-up) and Visit 3 (18-Months Follow-up) by
	Baseline DMD treatment – FAS Analysis Set (Limited to Visit 2)
Figure 15.2.4.1	Bar Plot of 6-Month Disability Improvement by Visit (Overall and by
	Baseline DMD) – FAS Analysis Set (Limited to Visit 2)
Table 15.2.5.1	MSIS29 results by Visit – FAS Analysis Set
Table 15.2.6.1	TSQM v1.4 results by Visit – FAS Analysis Set
Table 15.2.7.1	CCI
Table 15.3.1.1	Overview of Treatment-Emergent Adverse Events (TEAEs) – FAS
	Analysis Set
Table 15.3.1.2	TEAE by Primary System Organ Class (SOC) and Preferred Term (PT)
	– FAS Analysis Set
Table 15.3.1.3	Serious TEAE by Primary System Organ Class (SOC) and Preferred
	Term (PT) – FAS Analysis Set
Table 15.3.1.7	TEAE leading to Cladribine Permanent Discontinuation by Primary
	System Organ Class (SOC) and Preferred Term (PT) – FAS Analysis
	Set
Table 15.3.1.9	TEAE leading to death by Primary System Organ Class (SOC) and
	Preferred Term (PT) – FAS Analysis Set

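### The protocol asks for a running relapse total at each visit, but the SAP adds the visit counts, so the primary ARR is correct only if each count covers the interval since the previous visit

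*SAP*

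**What the plan says.** **Protocol 9.2.4** gives the same relapse item at Visits 1, 2, 3 and 4: "Total number of relapses while in study, up until this visit". The item collected at early termination is also a total over the time in study. Table 1 lists only a relapse count.

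**SAP 14.1.1** computes the year-2 ARR as the "sum of the number of MS relapses reported at Visit 3 and Visit 4 divided by the number of days" between the Visit 2 and Visit 4 dates, multiplied by 365.25. ARR at other visits uses the last two visits in the same way, "except for ARR at Visit 1 for which only the last 6-month data will be included".

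**SAP 14.2.1** computes the 1-year ARR from the "sum of the number of MS relapses from Visit 1 and Visit 2" over the days from cladribine start to Visit 2.

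Neither SAP section subtracts an earlier count or states what period a visit's count covers. SAP 7 declares: "There are no changes to the analyses planned per protocol". The eCRF page is named in SAP 16.4.1 as "MRI and Relapse Count", but its field definition is not given.

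**The concern.** A running total at Visit 4 already contains every relapse counted at Visit 3, and both contain everything from the first year. Adding them counts year-1 and early year-2 relapses twice, over a denominator that covers year 2 only. A patient with one relapse at month 3 and none afterwards would get a year-2 ARR of about 2, when the true value is 0.

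Under SAP 9 the primary outcome is the only confirmatory test. The pre-baseline ARR comes from a separate 12-month historical count and would not be inflated, so the error would run in one direction, against showing a reduction. The same sums feed the by-visit ARR table, the subgroup analyses, the LOCF analysis (where "the last available ARR from previous visits will be used for the analysis") and the interim output titled "ARR comparison between Baseline and 12-Months after start Cladribine". The planned sensitivity analyses would not reveal it: LOCF reuses the same derived ARR, and BOCF changes only missing values.

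**Working it through.** The plan states no ARR, and the sample-size assumptions are blacked out, so there is no plan figure to reproduce. The visit times (months 6, 12, 18 and 24) are from SAP 9.5 and the formulas from SAP 14.1.1 and 14.2.1. All relapse rates below are assumptions.

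**Algebra.** Let a, b, c, d be the relapses in the four successive 6-month periods. Running totals are N1 = a, N2 = a+b, N3 = a+b+c, N4 = a+b+c+d.

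| ARR | Correct numerator | SAP sum on running totals | Ratio at a constant yearly rate L (0.5L per period) |
|---|---|---|---|
| Year 2 (primary) | c+d | N3+N4 = 2a+2b+2c+d | 3.5L / L = 3.5 |
| Year 1 (secondary) | a+b | N1+N2 = 2a+b | 1.5L / L = 1.5 |
| Visit 3 | b+c | N2+N3 = 2a+2b+c | 2.5L / L = 2.5 |
| Visit 1 | a | N1 = a | 1 (unaffected) |

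If the fields hold interval counts, the SAP sums are c+d and a+b, which are correct.

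**Break-even.** The computed mean change is zero when 3.5 × post = pre, so post/pre = 1/3.5 = 0.286. That is a true reduction of 1 − 0.286 = 71%. Any smaller reduction is computed as an increase.

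**Unequal rates.** With 0.3 in year 1 and 0.1 in year 2, the sum is 2(0.3) + 2(0.05) + 0.05 = 0.75 against a true 0.1, a ratio of 7.5. With 0.1 then 0.3, it is 0.2 + 0.3 + 0.15 = 0.65 against 0.3, a ratio of 2.2. The factor 3.5 therefore holds only for a constant rate.

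**Effect on the test if the fields are cumulative.** Assumptions: pre-baseline ARR 1.0, n = 200, Poisson counts, exact 12-month intervals, Wilcoxon signed-rank at two-sided 5%, 2,000 simulated trials per rate.

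| True post-baseline ARR | 0.1 | 0.2 | 0.3 | 0.5 |
|---|---|---|---|---|
| True mean change | −0.90 | −0.80 | −0.70 | −0.50 |
| Computed change, primary (3.5 × ARR − 1) | −0.65 | −0.30 | +0.05 | +0.75 |
| Significant reduction, primary (100% if counted correctly) | 100% | about 80% | about 1% | 0% |
| Significant increase, primary | 0% | 0% | 4% | 99.9% |
| Computed change, 1-year (1.5 × ARR − 1) | −0.85 | −0.70 | −0.55 | −0.25 |
| Significant reduction, 1-year | 100% | 100% | 100% | 68% |

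The primary result depends on the assumed pre-baseline rate (800 trials per cell):

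| Pre-baseline ARR | 0.8 | 1.0 | 1.2 | 1.5 |
|---|---|---|---|---|
| Significant reduction, true ARR 0.2 | 18% | 80% | 99.5% | 100% |
| Significant reduction, true ARR 0.3 | 0% | 1% | 26% | 95% |

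At pre-baseline 1.0 (1,000 trials), the row 100% / 80% / 1% / 0% is unchanged with gamma-Poisson counts (variance 0.5). It becomes 100% / 88% / 1% / 0% with n = 242.

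**Differencing the wrong kind of field.** If the fields are interval counts, Visit 4 minus Visit 2 is d − b. It averages about 0 whatever the true rate, and is negative in 5% / 9% / 12% / 18% of patients at rates 0.1 / 0.2 / 0.3 / 0.5. The field must be identified before the formula is changed.

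**The case against.** The strongest counter-argument is that the SAP author probably had interval counts in mind. The SAP is the later document and names eCRF pages. Its Visit 2 to Visit 4 denominator, its use of the last two visits and its reference to the last six months of data make sense only for interval counts. Protocol 9.2.4 is a list of assessments, not a field specification. On that reading the SAP arithmetic is right and the protocol bullet is loosely worded. SAP 7 adds little, because Protocol 9.7 gives no ARR formula from which the SAP could depart.

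There are also controls that could catch the problem. SAP 6 plans a data review meeting and a dry run before lock, and both interims list the relapse counts. Under cumulative entry a patient's count can never fall. Under interval entry at an assumed ARR of 0.2, about 25% of patients would show a fall somewhere across Visits 1 to 4.

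Much of this stands. Bias in the final result is conditional on an eCRF field that cannot be seen here. The Visit 1 ARR, and LOCF values carried from it, are correct under either reading. The interim ARR outputs carry only the 1.5 factor. But the conflict itself remains. No section says which count is collected, and none instructs anyone to check. Even if the field is interval, sites hold a protocol that asks for totals and some may enter totals.

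**Conclusion.** The concern holds. The two documents define the input to the only confirmatory endpoint in incompatible ways, and carrying out both texts as written gives a wrong primary ARR. That much needs no assumption about rates.

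Whether the final data would be biased depends on the eCRF field. If it is cumulative, the primary ARR is inflated 3.5 times and the 1-year ARR 1.5 times at a constant rate, and the primary conclusion can be lost or reversed at plausible but assumed rates. If it is interval, there is no bias from the formula, and the error is in the protocol wording. One of the two documents has to change in either case, and this should be settled before database lock.

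**What to change.** 1. Before database lock, establish from the eCRF relapse field and its completion instructions whether it is cumulative or since the last visit. Use the planned relapse-count listing as a check: a count that falls between visits shows interval entry for that patient.

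2. **If cumulative:** in SAP 14.1.1 use the Visit 4 count minus the Visit 2 count for year 2, and in SAP 14.2.1 use the Visit 2 count for year 1. Keep the denominators. Carry the change through the by-visit, LOCF, subgroup and interim outputs, and check for sites that entered interval counts. Also align the year-1 count with cladribine start, which begins the denominator. Time in study starts at consent (Protocol 9.2.3), which can fall before or after the first dose (Protocol 9.2.2).

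3. **If interval:** keep the SAP sums, state in the SAP that each count is new relapses since the previous visit, correct the item at Visits 1 to 4 in Protocol 9.2.4, and query sites for totals entered in an interval field.

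**Cost:** one check of a field definition. The cumulative case then needs SAP wording and a one-line derivation, with no new data. The interval case needs wording in both documents and a data query.
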